5.2.2 Dose Modification (Escalation/Titration/Other)

For individual subjects, dose delays and modifications of trial treatment will be based on treatment-related toxicity, laboratory test results prior to treatment administration, and clinical assessments during the previous cycle and on the day of treatment. Guidelines for dose delay and dose modification are described below and are applicable to the start of each cycle as well as during the cycle if treatment-related toxicities occur.

5.2.2.1 MK-8353 Dose Modifications

Criteria for Dose Delay

Except in Cycle 1 in which dosing can be delayed up to 2 weeks, dosing of MK-8353 should be delayed for up to 3 weeks, until the AE is resolved to baseline status or \leq Grade 1 in case of:

- Any treatment-related hematological or nonhematological AE \geq Grade 3
- OR

- Any abnormal nonhematological laboratory value \geq Grade 3 that requires medical intervention, hospitalization, or persists for \geq 1 week, except for a clinically nonsignificant, treatable, or reversible laboratory abnormalities

Any \geq Grade 3 AE of nausea and/or vomiting, or anorexia if left untreated without medical intervention will not require a dose delay.

A reoccurring Grade 2 hematological or nonhematological AE, which in the opinion of the investigator is treatment-related and significant despite medical intervention, should be discussed with the Sponsor prior to any dose delay.

Subjects should be assessed weekly until the AE has resolved to baseline status or \leq Grade 1 and dosing resumes or the subject is discontinued from the study.

If treatment is delayed by more than 3 weeks (or by more than 2 weeks in Cycle 1) because of treatment-related toxicity, study treatment should be discontinued. However, subjects with evidence of clinical benefit may be allowed to continue treatment despite a treatment delay (for any reason) of more than 3 weeks, after discussion with the Sponsor.

Criteria for Dose Modification

Once a dose delay occurs, upon resolution of any treatment-related AE to baseline status or \leq Grade 1, the dose level of MK-8353 for the subsequent doses must be reduced 1 dose level.

Any dose level reduction will be permanent (ie, dose re-escalation is NOT allowed). No more than 2 dose level reductions will be allowed. Subjects who require further dose reductions or dose reductions below DL -1 should be discontinued from the study treatment.

Dose reductions are not permitted during the DLT evaluation period.

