DL3D	150	150 for Cycle 1, Day 1 to Day 14 (run-in), and Day 1 to Day 21 of subsequent cycles	200
DL4D	200	200 for Cycle 1, Day 1 to Day 14 (run-in), and Day 1 to Day 21 of subsequent cycles	200
DL5D	300	300 for Cycle 1, Day 1 to Day 14 (run-in), and Day 1 to Day 21 of subsequent cycles	200
DL6D	400	400 for Cycle 1, Day 1 to Day 14 (run-in), and Day 1 to Day 21 of subsequent cycles	200
DL7D	600	600 for Cycle 1, Day 1 to Day 14 (run-in), and Day 1 to Day 21 of subsequent cycles	200

* If 50 mg doses are not tolerable, doses of 10 mg and 30 mg may be explored.
** DL2A (150 mg daily) will be administered as a morning dose of 50 mg and an evening dose of 100 mg of MK-8353.
bid=twice daily; DL=dose level, IV=intravenous, q3w=once every 3 weeks; qd=once daily.

Each individual subject will be assigned to a single dose level of study drug. Intrasubject dose escalation is not allowed. Individual subject dose interruptions and/or dose decreases may be implemented based on toxicity as described in Section 5.2.2; however, dose adjustments should not be made during the DLT evaluation period without discussion with the Sponsor.

The decision to enroll subjects in the next dose level will be made by the Sponsor in consultation with the participating investigators after reviewing the safety and any available PK data of the previous dose level(s).

Subjects may continue on treatment until disease progression, unacceptable toxicity, investigator's decision to withdraw the subject, withdrawal of consent, development of an intercurrent condition precluding further administration of study treatment, pregnancy of the subject, failure to comply with dosing evaluations or other study requirements, or administrative reasons.

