5.2.1.5 Definition of Dose-limiting Toxicities

All toxicities will be graded using NCI CTCAE Version 4.0 based on investigator assessment (Appendix 12.7).

The DLT window of observation will be during Cycle 1 for Arms A, B, and C (21 days/3 weeks), and Cycles 1 and 2 for Arm D (35 days/5 weeks).

The occurrence of any of the following toxicities during the DLT window will be considered a DLT, if assessed by the investigator to be possibly, probably, or definitely related to study drug administration:

1. Grade 4 nonhematologic toxicity (not laboratory).
2. Grade 4 hematologic toxicity lasting ≥ 7 days, except thrombocytopenia
 - a. Grade 4 thrombocytopenia of any duration
 - b. Grade 3 thrombocytopenia associated with bleeding
3. Grade 3 nonhematologic toxicity (not laboratory) lasting >3 days despite optimal supportive care.
4. Any Grade 3 or Grade 4 nonhematologic laboratory value if:
 - Medical intervention is required to treat the subject, or
 - The abnormality leads to hospitalization, or
 - The abnormality persists for >1 week.
 - Exceptions:
 - Clinically nonsignificant, treatable, or reversible laboratory abnormalities (eg, liver function tests, uric acid)
5. Febrile neutropenia Grade 3 or Grade 4:
 - Grade 3 is defined as absolute neutrophil count (ANC) $<1000/\text{mm}^3$ with a single temperature of >38.3 degrees C (101 degrees F) or a sustained temperature of ≥ 38 degrees C (100.4 degrees F) for more than 1 hour
 - Grade 4 is defined as ANC $<1000/\text{mm}^3$ with a single temperature of >38.3 degrees C (101 degrees F) or a sustained temperature of ≥ 38 degrees C (100.4 degrees F) for more than 1 hour, with life-threatening consequences and urgent intervention indicated
6. Prolonged delay (>2 weeks) in initiating Cycle 2 due to treatment-related toxicity.
7. Any treatment-related toxicity that causes the subject to discontinue treatment during Cycle 1.
8. Missing $>25\%$ of MK-8353 doses as a result of drug-related AE(s) during the first cycle.
9. Grade 5 toxicity.

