5.2.1.6 Replacement of Subjects in Dose-limiting Toxicity Period

In order to fully evaluate the safety of the combination therapy in this study, all subjects enrolled must meet the criteria for evaluability for Cycle 1. Subjects are considered nonevaluable and will be replaced if:

- They are enrolled but not treated.

- They discontinue from the trial prior to completing all safety evaluations due to reasons other than drug-related AEs.
- They received <90% of the total pembrolizumab infusion in Cycle 1 (eg, because the infusion had to be discontinued due to an infusion reaction) and did not experience a drug-related event.
- They received $\leq 75\%$ of MK-8353 doses intended for the trial during Cycle 1 and did not experience a drug-related event.
- They must take a prohibited concomitant medication during Cycle 1, unless this medication is used to treat a study drug-related AE.
- They must undergo medical / surgical procedures or have logistical issues not related to study therapy (eg, elective surgery, unrelated medical events) during Cycle 1.

Subjects discontinuing within 21 days (or 35 days for Arm D) of the first dose due to reasons unrelated to study treatment will not be considered evaluable for DLTs and may be replaced. Subjects with a DLT within 21 days (or 35 days for Arm D) of the first dose should not be replaced.

Nonevaluable subjects will not be counted toward the (Part 1 or Part 2) total for DLT evaluation.

Subjects who experience a DLT in the DLT window should be discontinued from the trial. However, if in the opinion of the investigator, the subject is deriving clinical benefit from the study treatment, the subject may be allowed to continue on the trial after discussion with the Sponsor.

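### The dose at which a subject restarts MK-8353 inside the DLT window is not settled, and a subject reduced there for a non-DLT event would by default count as DLT-free at the assigned dose

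*Combined protocol and SAP*

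**What the plan says.** Four rules bear on a dose decrease inside the DLT window (21 days in Arms A to C, 35 days in Arm D).

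- **Section 5.2.1.4** says "Individual subject dose interruptions and/or dose decreases may be implemented based on toxicity as described in Section 5.2.2". It then adds that "dose adjustments should not be made during the DLT evaluation period without discussion with the Sponsor".
- **Section 5.2.2** makes its delay and modification guidance "applicable to the start of each cycle as well as during the cycle if treatment-related toxicities occur".
- **Section 5.2.2.1** calls for MK-8353 to be held for any treatment-related event of Grade 3 or above, with one specific limit: "Except in Cycle 1 in which dosing can be delayed up to 2 weeks". After a delay and recovery, "the dose level of MK-8353 for the subsequent doses must be reduced 1 dose level". That sentence has no Cycle 1 exception.
- **Section 5.2.2.1** closes with "Dose reductions are not permitted during the DLT evaluation period".

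Three rules decide how a subject is counted.

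- **Section 5.2.1.5, criterion 8** makes it a DLT to miss more than 25% "of MK-8353 doses as a result of drug-related AE(s) during the first cycle". It is about missed doses. A lowered dose is not on the DLT list.
- **Section 5.2.1.6** makes a subject nonevaluable who received 75% or less "of MK-8353 doses intended for the trial during Cycle 1 and did not experience a drug-related event". A subject who did have a drug-related event is not removed by this rule.
- **Section 8.5.1** includes treated subjects observed for 21 (or 35) days, or with an earlier DLT. It moves subjects to the treatment actually received only after administration errors.

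**The concern.** Take a subject who is held in Cycle 1 for a short Grade 3 event and recovers before Day 21. One site could restart at the assigned dose, citing the ban. Another could restart one level lower, citing the must-reduce sentence or a discussion with the Sponsor under Section 5.2.1.4. The protocol does not say which is right.

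The DLT rate is the primary endpoint (Section 8.1) and the input to the Table 3 decisions (Section 5.2.1.2). A subject who took a lower dose for part of the window could enter both as a full DLT-free observation at a dose not taken throughout. That error can only lower the apparent DLT rate at the assigned level.

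**Working it through.** **1. Can an in-window reduction happen without a DLT?** Section 5.2.2.1 asks for a hold for any treatment-related Grade 3 event. Under criterion 3 of Section 5.2.1.5, Grade 3 nonhematologic, nonlaboratory toxicity is a DLT only if it lasts more than 3 days. On a once-daily schedule, 5 missed doses of 21 is 5/21 = 23.8%, which does not meet criterion 8. Six missed is 6/21 = 28.6%, which does. So a Grade 3 event of 3 days or less, with up to 5 doses missed, calls for a hold and is not a DLT.

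**2. How would that subject be counted if reduced?** No missed-dose DLT, because lowered doses are not missed doses. Not nonevaluable under the 75% rule, because a drug-related event occurred. Included under Section 8.5.1 after 21 days of observation, at the assigned level. The result is one DLT-free subject at the assigned dose. A subject whose event meets any of criteria 1 to 9 is a DLT whatever the dose change, so the gap is confined to non-DLT events.

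**3. How different is the exposure?** Assume Arm B, Days 5 to 7 missed (3/21 = 14.3%), restart on Day 8.

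| Assigned, restart dose | mg taken | Planned mg | Share |
|---|---|---|---|
| 600 mg, restart at 400 mg | 4×600 + 14×400 = 8,000 | 21×600 = 12,600 | 63.5% |
| 1200 mg, restart at 900 mg | 4×1200 + 14×900 = 17,400 | 21×1200 = 25,200 | 69.0% |
| Either, restart at assigned dose | 18 of 21 doses | 21 doses | 85.7% |

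The part due to the reduction is 85.7 − 63.5 = 22.2 points, or 85.7 − 69.0 = 16.7 points. A restart on Day 15 after missing Days 12 to 14 gives (11×600 + 7×400)/12,600 = 74.6% in the 600 mg case, so the reduction accounts for 11.1 points.

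**4. Reproduce Table 3.** Inputs from Table 3 and its notes: target 30%, Beta(1,1) prior, ε1 = ε2 = 0.05. With t DLTs in n subjects, the posterior is Beta(1+t, 1+n−t). Divide the posterior probability of each interval (0 to 0.25, 0.25 to 0.35, 0.35 to 1) by its length and take the largest. DU applies if P(rate > 0.30) exceeds 0.95. That cut-off is an assumption, as the documents give none. All 78 cells in rows 0 to 6 match. Cut-offs of 0.90, 0.94 and 0.96 each miss at least one cell.

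**5. Effect of one subject on a decision.**

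- 1/6, Beta(2,6): 0.5551/0.25 = 2.22 (Escalate), (0.7662 − 0.5551)/0.10 = 2.11 (Stay), 0.2338/0.65 = 0.36 (De-escalate). Decision: Escalate.
- 2/6, Beta(3,5): 0.2436/0.25 = 0.97, (0.4677 − 0.2436)/0.10 = 2.24, 0.5323/0.65 = 0.82. Decision: Stay.
- If the subject is instead dropped and not yet replaced, 1/5 is also Stay in Table 3.

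**6. Effect on the rate at n = 14.** Raw rates before any pooling: 4/14 = 28.6% and 5/14 = 35.7%, a difference of 1/14 = 7.1 points. The 80% credible intervals under Beta(1,1), as Section 8.6.2 specifies, are 17.2% to 46.4% for 4/14 (Beta(5,11)) and 22.6% to 53.2% for 5/14 (Beta(6,10)). They overlap widely.

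Steps 5 and 6 show what any one reclassified subject does in this design. They do not estimate how often reductions in the window occur.

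**The case against.** The best defence is that the sections can be reconciled. Section 5.2.1.4 permits decreases only by reference to Section 5.2.2, where the ban sits. Its second clause is a restriction, and dose adjustments can mean interruptions. The ban closes the same subsection as the must-reduce sentence and can be read as limiting it. Read this way, a subject either restarts at the assigned dose or stays on hold, and no reduced subject reaches the DLT count. That reading is reasonable. What survives is that it has to be inferred, and that no text states the restart dose.

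There are also safeguards. The Sponsor would know of any reduction made under Section 5.2.1.4, escalation follows review of safety and available PK data, and Section 5.2.1.2 bases dose selection on all the data. These allow for a reduced subject informally. They do not alter the counted rate, for which there is no rule.

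A reader might infer that the plan authorises in-window reductions and counts every reduced subject as DLT-free, so that the DLT rates are biased. The documents do not support that: the ban is explicit, subjects meeting a DLT criterion are counted, and no frequency is given. A reader might also see a conflict in the Grade 3 rash guidance in Section 5.6.1.1. It offers interruption as an alternative to reduction, so it can be followed without breaching the ban.

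**Conclusion.** The point stands in conditional form. The text leaves open the restart dose inside the DLT window. If a subject is reduced there for a drug-related event that is not a DLT, the counting rules by default record a DLT-free subject at the assigned dose, and the error lowers that level's DLT rate. If the ban is applied strictly, nothing is miscounted.

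The size is known only per subject: one Table 3 decision at some counts (1/6 against 2/6), and 7.1 points on the raw rate at n = 14. The documents allow no estimate of frequency. The illustrations assume that the subject would be recoded as a DLT, and the Table 3 reproduction assumes the 0.95 cut-off. Severity lies between a minor clarification and a change that should be made. The case for making it is that it concerns the primary endpoint and takes few words.

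**What to change.** 1. **Let the ban govern the window.** In Section 5.2.2.1, except the DLT evaluation period from the must-reduce sentence. In Section 5.2.1.4, limit what may be done in the window after Sponsor discussion to interruptions. State that a subject who restarts inside the window does so at the assigned dose, and otherwise stays on hold or stops. Any reduction waits until the window closes.
2. **Set a counting rule as a backstop.** In Sections 5.2.1.6 and 8.5.1, state that a subject nevertheless reduced in the window is not counted as DLT-free at the assigned level. Reduced for drug-related toxicity: a DLT. Reduced for any other reason: nonevaluable and replaced.
3. **Close the Arm D gap.** Criteria 7 and 8 refer to Cycle 1, but the Arm D window includes Cycle 2, where the combination starts. Extend both to the full 35 days. The denominator for criterion 8 needs stating: applied per cycle, it triggers at 4/14 or 6/21 (both 28.6%); pooled over 35 doses, it would need 9 (25.7%) and would weaken the present Cycle 1 trigger.

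The cost is a phrase or sentence in each of Sections 5.2.1.4, 5.2.1.5, 5.2.1.6, 5.2.2.1 and 8.5.1, plus a few subjects if any are replaced. The downside is clinical: a subject may restart at the full assigned dose after recovery to Grade 1 or less. An investigator unwilling to do that can hold or stop. Stopping for toxicity in Cycle 1 is a DLT, but a short hold late in the window (Days 17 to 21, 5/21 = 23.8%) still is not.

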5.2.2.2 Immune-Related Events and Dose Modification (Withhold, Treat, Discontinue)

Dose Modification and Toxicity Management for Immune-related AEs Associated with Pembrolizumab

AEs associated with pembrolizumab exposure may represent an immune-related response. These irAEs may occur shortly after the first dose or several months after the last dose of pembrolizumab treatment and may affect more than one body system simultaneously. Therefore, early recognition and initiation of treatment is critical to reduce complications. Based on existing clinical study data, most irAEs were reversible and could be managed with interruptions of pembrolizumab, administration of corticosteroids and/or other supportive care. For suspected irAEs, ensure adequate evaluation to confirm etiology or exclude other causes. Additional procedures or tests such as bronchoscopy, endoscopy, skin biopsy may be included as part of the evaluation. Based on the severity of irAEs, withhold or permanently discontinue pembrolizumab and administer corticosteroids.

Dose Modification and Toxicity Management Guidelines for irAEs associated with pembrolizumab monotherapy, coformulations, or IO combinations are provided in [Table 5](#).

Table 5 Dose Modification and Toxicity Management Guidelines for Immune-related Adverse Events Associated with Pembrolizumab Monotherapy, Coformulations or IO Combinations

General instructions:				
irAEs	Toxicity Grade (CTCAEv4.0)	Action With Pembrolizumab Monotherapy, Coformulations or IO Combinations	Corticosteroid and/or Other Therapies	Monitoring and Follow-up
Pneumonitis	Grade 2	Withhold	
 Administer corticosteroids (initial dose of 1-2 mg/kg prednisone or equivalent) followed by taper 	
 Monitor participants for signs and symptoms of pneumonitis Evaluate participants with suspected pneumonitis with radiographic imaging and initiate corticosteroid treatment Add prophylactic antibiotics for opportunistic infections
	Recurrent Grade 2 or Grade 3 or 4	Permanently discontinue		
Diarrhea / Colitis	Grade 2 or 3	Withhold	
 Administer corticosteroids (initial dose of 1-2 mg/kg prednisone or equivalent) followed by taper 	
 Monitor participants for signs and symptoms of enterocolitis (ie, diarrhea, abdominal pain, blood or mucus in stool with or without fever) and of bowel perforation (ie, peritoneal signs and ileus) Participants with \geqGrade 2 diarrhea suspecting colitis should consider GI consultation and performing endoscopy to rule out colitis Participants with diarrhea/colitis should be advised to drink liberal quantities of clear fluids. If sufficient oral fluid intake is not feasible, fluid and electrolytes should be substituted via IV infusion.
	Recurrent Grade 3 or Grade 4	Permanently discontinue		

irAEs	Toxicity Grade (CTCAEv4.0)	Action With Pembrolizumab Monotherapy, Coformulations or IO Combinations	Corticosteroid and/or Other Therapies	Monitoring and Follow-up
AST / ALT Elevation or Increased Bilirubin	Grade 2	Withhold	
 Administer corticosteroids (initial dose of 0.5-1 mg/kg prednisone or equivalent) followed by taper 	
 Monitor with liver function tests (consider weekly or more frequently until liver enzyme value returned to baseline or is stable)
	Grade 3 or 4	Permanently discontinue	
 Administer corticosteroids (initial dose of 1-2 mg/kg prednisone or equivalent) followed by taper 	
T1DM or Hyperglycemia	New onset T1DM or Grade 3 or 4 hyperglycemia associated with evidence of β -cell failure	Withhold ^a	
 Initiate insulin replacement therapy for participants with T1DM Administer anti-hyperglycemic in participants with hyperglycemia 	
 Monitor participants for hyperglycemia or other signs and symptoms of diabetes
Hypophysitis	Grade 2	Withhold	
 Administer corticosteroids and initiate hormonal replacements as clinically indicated 	
 Monitor for signs and symptoms of hypophysitis (including hypopituitarism and adrenal insufficiency)
	Grade 3 or 4	Withhold or permanently discontinue ^a		
Hyperthyroidism	Grade 2	Continue	
 Treat with non-selective beta-blockers (eg, propranolol) or thionamides as appropriate 	
 Monitor for signs and symptoms of thyroid disorders
	Grade 3 or 4	Withhold or Permanently discontinue ^a		

irAEs	Toxicity Grade (CTCAEv4.0)	Action With Pembrolizumab Monotherapy, Coformulations or IO Combinations	Corticosteroid and/or Other Therapies	Monitoring and Follow-up
Hypothyroidism	Grade 2-4	Continue	
 Initiate thyroid replacement hormones (eg, levothyroxine or liothyronine) per standard of care 	
 Monitor for signs and symptoms of thyroid disorders
Nephritis and renal dysfunction	Grade 2	Withhold	
 Administer corticosteroids (prednisone 1-2 mg/kg or equivalent) followed by taper 	
 Monitor changes of renal function
	Grade 3 or 4	Permanently discontinue		
Myocarditis	Grade 1	Withhold	
 Based on severity of AE administer corticosteroids 	
 Ensure adequate evaluation to confirm etiology and/or exclude other causes
	Grade 2, 3 or 4	Permanently discontinue		
All Other irAEs	Persistent Grade 2	Withhold	
 Based on severity of AE administer corticosteroids 	
 Ensure adequate evaluation to confirm etiology or exclude other causes
	Grade 3	Withhold or discontinue ^b		
	Recurrent Grade 3 or Grade 4	Permanently discontinue		

AE(s) adverse event(s); ALT alanine aminotransferase; AST aspartate aminotransferase; CTCAE Common Terminology Criteria for Adverse Events; DRESS Drug Rash with Eosinophilia and Systemic Symptom; GI gastrointestinal; IO immuno oncology; ir immune related; IV intravenous; SJS Stevens Johnson Syndrome; T1DM type 1 diabetes mellitus; TEN Toxic Epidermal Necrolysis; ULN upper limit of normal.

Note: Non-irAE will be managed as appropriate, following clinical practice recommendations.

^a The decision to withhold or permanently discontinue pembrolizumab monotherapy, coformulations or IO combinations is at the discretion of the investigator or treating physician. If control achieved or ≤ Grade 2, pembrolizumab monotherapy, coformulations or IO combinations may be resumed.

^b Events that require discontinuation include, but are not limited to: Guillain Barre Syndrome, encephalitis, myelitis, DRESS, SJS, TEN and other clinically important irAEs (eg, vasculitis and sclerosing cholangitis).

Dose Modification and Toxicity Management of Infusion Reactions Related to Pembrolizumab

Pembrolizumab may cause severe or life-threatening infusion reactions including severe hypersensitivity or anaphylaxis. Signs and symptoms usually develop during or shortly after drug infusion and generally resolve completely within 24 hours of completion of infusion. Dose modification and toxicity management guidelines on pembrolizumab-associated infusion reaction are provided in [Table 6](#).

Table 6 Pembrolizumab Infusion Reaction Dose Modification and Treatment Guidelines

NCI CTCAE Grade	Treatment	Premedication at Subsequent Dosing
Grade 1 Mild reaction; infusion interruption not indicated; intervention not indicated	Increase monitoring of vital signs as medically indicated until the subject is deemed medically stable in the opinion of the investigator.	None
Grade 2 Requires therapy or infusion interruption but responds promptly to symptomatic treatment (eg, antihistamines, NSAIDs, narcotics, IV fluids); prophylactic medications indicated for ≤ 24 hrs	Stop Infusion. Additional appropriate medical therapy may include but is not limited to: 
IV fluidsAntihistaminesNSAIDsAcetaminophenNarcotics Increase monitoring of vital signs as medically indicated until the subject is deemed medically stable in the opinion of the investigator. If symptoms resolve within 1 hour of stopping drug infusion, the infusion may be restarted at 50% of the original infusion rate (eg, from 100 mL/hr to 50 mL/hr). Otherwise dosing will be held until symptoms resolve and the subject should be premedicated for the next scheduled dose. Subjects who develop Grade 2 toxicity despite adequate premedication should be permanently discontinued from further study drug treatment.	Subject may be premedicated 1.5h (± 30 minutes) prior to infusion of pembrolizumab with: Diphenhydramine 50 mg po (or equivalent dose of antihistamine). Acetaminophen 500 to 1000 mg po (or equivalent dose of analgesic).


Grades 3 or 4
 
Grade 3: Prolonged (ie, not rapidly responsive to symptomatic medication and/or brief interruption of infusion); recurrence of symptoms following initial improvement; hospitalization indicated for other clinical sequelae (eg, renal impairment, pulmonary infiltrates)
 
Grade 4: Life-threatening; pressor or ventilatory support indicated
	
Stop Infusion. Additional appropriate medical therapy may include but is not limited to:
 
• Epinephrine**• IV fluids• Antihistamines• NSAIDs• Acetaminophen• Narcotics• Oxygen• Pressors• Corticosteroids 
Increase monitoring of vital signs as medically indicated until the subject is deemed medically stable in the opinion of the investigator.
 
Hospitalization may be indicated.
 
**In cases of anaphylaxis, epinephrine should be used immediately.
 
Subject is permanently discontinued from further study drug treatment.
	No subsequent dosing

Appropriate resuscitation equipment should be available at the bedside and a physician readily available during the period of drug administration.
 
For further information, please refer to the NCI CTCAE, version 4.0 at http://ctep.cancer.gov
 
CTCAE=Common Toxicity Criteria for Adverse Events; IV=intravenous; NCI=National Cancer Institute; NSAIDs=nonsteroidal anti-inflammatory drugs; po=per os (by mouth).
		

Dosing interruptions are permitted after Cycle 1 in the case of medical/surgical events or logistical reasons not related to study therapy (eg, elective surgery, unrelated medical events, subject vacation, and/or holidays). Subjects should be placed back on study therapy within 3 weeks of the scheduled interruption, unless otherwise discussed with the Sponsor. The reason for interruption should be documented in the subject's study record.

